### 9.4.3.2. Action Taken for Adverse Events

For each reported adverse event, an Investigator must document the action taken according to the following criteria:

- No action
- Concomitant medication

Aptinyx Confidential

- Hospitalization or prolongation of hospitalization
- Study discontinuation
- Nondrug therapy
- Other (specify)

The Investigator must also document the action taken with study drug (as a result of a given adverse event) according to the following criteria:

- Dose not changed
- Study drug interrupted
- Study drug withdrawn
- Not applicable
- Unknown

#### 9.4.3.3. Outcome for Adverse Events

Adverse events should be followed until resolution. For each reported adverse event, the Investigator must document the outcome according to the following criteria:

- Fatal
- Not recovered/not resolved
- Recovered/resolved
- Recovered/resolved with sequelae
- Recovering/resolving
- Unknown

### 9.5. Serious Adverse Events

Serious adverse event reporting will begin at the time informed consent is obtained and will end 30 days after the last dose of study drug. Serious adverse events are reported to the Sponsor or designee using the provided form by email or fax to the following email address or fax number, respectively:

A serious adverse event is any adverse event occurring at any dose that results in any of the following outcomes:

- Death: "Death" is an outcome and is NOT the adverse event. In the event of death, the cause of death should be recorded as the adverse event. The only exception is "sudden death" when the cause is unknown.
- Is a life-threatening experience: Life-threatening adverse events include any adverse drug experience that, in the view of the Investigator, places the subject at immediate risk of

death from the reaction as it occurs. It does not include a reaction that, had it occurred in a more serious form, might have caused death.

- Requires inpatient hospitalization or prolongation of existing hospitalization.
- Results in a persistent or significant disability/incapacity: Disability is defined as a substantial disruption in a person's ability to conduct normal life functions.
- Results in a congenital anomaly/birth defect.
- Additionally, important medical events that may not result in death, be life-threatening, or require hospitalization may be considered a serious adverse event when, based upon appropriate medical judgment, they may jeopardize the subject and may require medical or surgical intervention to prevent 1 of the outcomes listed previously (e.g., allergic bronchospasm requiring intensive treatment in an emergency room or at home).

All serious adverse events that result in death or are life-threatening, regardless of causal relationship, must be reported to the Sponsor-designated Medical Monitor within 24 hours of the site's knowledge of the event. A copy of the initial serious adverse event report must be received within 1 business day.

All other serious adverse events or other events reportable to the United States Food and Drug Administration (FDA) and/or IRB will be forwarded to the Sponsor-designated Medical Monitor within 1 business day.

Any reported cases of COVID-19 that meet the SAE criteria above should be reported as per the protocol's defined SAE process.

The serious adverse event report should provide as much of the required information as is available at the time. The following minimum information is required for reporting a serious adverse event: subject identification, reporting source, and an event outcome. Supplemental information may be transmitted using a follow-up report and should not delay the initial report. Aptinyx may contact the investigational site to solicit additional information or to follow-up on the event.

If there is any doubt whether the information constitutes a serious adverse event, the information will be treated as a serious adverse event for the purposes of this protocol. Serious adverse event reporting will begin at the time of consent and will end 30 days after the last dose.

All relevant documentation pertaining to a serious adverse event (e.g., additional diagnostic tests, consultation reports, discharge summaries, and postmortem reports) will be provided to the Sponsor-designated Medical Monitor in a timely manner. Serious adverse events will be followed until resolution or return to baseline (when worsening of a pre-existing condition is reported). If a serious adverse event does not return to baseline but reaches a stable situation that is not expected to change, this may be documented on the serious adverse event form.

The Sponsor may break the treatment code for subjects who experience a serious adverse event in order to determine if the individual case or group of cases requires expedited regulatory reporting. Individual treatment codes will be available to limited staff who are responsible to break codes for reporting purposes.

For each SAE, the Investigator and Sponsor will independently assess whether there is a reasonable possibility that the event may have been caused by the study drug ("drug-related"). The Sponsor will evaluate each drug-related SAE to determine if the event was unexpected. If the SAE is assessed to be both drug-related and unexpected, the Sponsor or designee will notify all

Investigators, and will report it to the appropriate regulatory authorities as required by applicable local regulations. The Sponsor or designee will report SAEs, including narratives, to the U.S. FDA and local regulatory authorities as required by 21 CFR 312.32 and the International Conference on Harmonisation (ICH) Guideline for Good Clinical Practice. The Investigator is responsible for notifying his/her respective IRB.

# 9.5. Other Reportable Events

All pregnancies occurring during the study must be followed for information regarding the course of pregnancy, delivery, and condition of the newborn. Follow-up should be provided by the Investigator to the Sponsor-designated Medical Monitor in a timely manner. When the newborn is healthy, further follow-up is not necessary. Male subjects must inform the Investigator if their partner becomes pregnant during the study.

### **10.** SCHEDULE OF PROCEDURES

The schedule of procedures is summarized in Table 3.

### 10.1. Visit 1 and Screening Period (Week -4 to Week -1)

The subject will be asked to provide written, informed consent for this study before any required procedures are performed. This study may employ electronic informed consent. Electronic or digital signatures (compliant with 21 CFR § 11 regulations for collecting and storing digital signatures) may be captured indicating the patient's willingness to participate in the clinical trial. The use of electronic informed consent supplements the interaction between the participant and the research staff, and it provides an opportunity for remote conduct of study activities in the setting of the COVID-19 Health Emergency. Subjects will also be asked by site staff to sign an additional consent for their inclusion in a secure, proprietary research subject database maintained by Verified Clinical Trials (VCT) [Verified Clinical Trials, Garden City, NY]. The database will use partially identified subject information to review subjects' research study history within the database.

Subjects who meet any of the following criteria will not be eligible for continued screening: current enrollment in another study, concurrent screening at another research site, violation of the required number of half-lives of the investigational product of the prior research study, violation of the washout period between studies, incorrect age for the NYX-2925-2008 study, or previous randomization into a clinical trial of NYX-2925. Employees, contractors, or volunteers of the study site, CRO, or Aptinyx, or relatives of any employee, contractor, or volunteer of the study site, CRO, or Aptinyx are not eligible to participate. Serious adverse event collection begins after the informed consent is obtained and adverse event collect begins after study drug administration.

There may be up to three components in the screening period for this study: 1) After providing informed consent, subjects will participate in a screening visit where medical history, concomitant medications, scales, and eligibility to participate will be assessed; 2) Subjects who meet eligibility requirements and are taking an analgesic medication for pain related to diabetic peripheral neuropathy will then be required to discontinue their analgesia and "wash out" from one to four weeks (see Section 15.1 of the protocol for Disallowed Analgesic and Other Medications).

Subjects taking no concomitant analgesic medication for their painful diabetic neuropathy at Visit 1 may directly begin Week -1 of the Screening Period; 3) During this time, subjects will be provided a handheld device to record their pain and rescue medication use.

Aptinyx Confidential

Prior to recording their first pain score in the handheld device, each subject will undergo educational training on Accurate Pain Reporting (APR®) and Placebo Response Reduction (PRR®) via an electronic learning management system, aLearn® [Analgesic Solutions, Wayland, MA].

After the informed consents are signed, the following procedures and assessments should be completed at Visit 1:

- Demographic characteristics (age, sex, race, and ethnicity)
- Medical history, including history of Type 2 diabetes and history of painful DPN
- Prior (within last 30 days) and concomitant medications
- S-STS
- Adverse events
- Confirmation of diabetic peripheral neuropathy by the following assessments:
  - MNSI
  - MDT
- PGI-S
- Height and body weight
- Vital signs (blood pressure and pulse after sitting or lying supine for at least five (5) minutes)
- Complete physical examination, including comprehensive neurological examination
- Triplicate ECG after at least five (5) minutes in supine position with a minimum of a two minute interval between ECGs
- Fasting (8 hours) blood samples for hematology, serum chemistry, triglycerides, HbA1c, and a thyroid panel (TSH, T3, T4 and free T4)
- Blood samples for screening for HIV, hepatitis B and hepatitis C
- Urine sample for urinalysis
- Urine pregnancy test for females of childbearing potential
- Urine drug screen

Eligible subjects who meet all the inclusion criteria and none of the exclusion criteria will enter the 1- to 4-week Screening Period. The following procedures and assessments will be performed:

- Subjects will discontinue all analgesic treatments for neuropathic pain associated with diabetic peripheral neuropathy, and complete daily pain diaries. The duration of their Screening Period will depend upon the analgesic treatment that is being discontinued, but the total duration of the Screening Period cannot exceed 4 weeks (see Section 15.1 of the protocol for Disallowed Analgesic and Other Medications). Subjects already taking no concomitant analgesic medication may directly begin Week -1 of the Screening Period.
- Subjects will be provided a handheld device for pain reporting, and as a method for ensuring consistency and reliability of pain scoring, subjects will be instructed at all study visits how to record their pain score on the device and rescue medication use. Subjects will

be educated at screening and reminded at other visits on appropriate expectations for their participation in a clinical study and the importance of consistently and accurately reporting their pain throughout the study. On each day preceding the Baseline Visit: (Week 0/Visit 2), subjects will record the following on the handheld device:

- At bedtime: average pain intensity, worst pain intensity, average pain upon walking, and rescue medication use during the past 24 hours
- Upon waking: DSIS
- Subjects will be dispensed acetaminophen to be used as rescue medication and will be instructed to take no more than 2 g/day (one to two 500 mg tablets every 6 hours as needed up to 4 tablets total) for DPN related pain.

### 10.2. Baseline Visit: Week 0/Visit 2

At Week 0/Visit 2 (Baseline Visit), the following procedures and assessments will be performed/assessed prior to randomization:

- Concomitant medication use
- PGI-S
- S-STS
- Adverse events
- Vital signs (blood pressure and pulse after sitting or lying supine for at least 5 minutes)
- ECG after at least five (5) minutes in supine position
- Fasting (8 hours) blood samples for hematology and serum chemistry
- Urine sample for urinalysis
- Urine pregnancy test for females of childbearing potential
- Urine drug screen
- Rescue medication return, assessment of appropriate use by inventory of returned tablets, as well as by subject interview
- Verify eligibility with inclusion and exclusion criteria

Pain scores reported by subjects during the Screening Period will be evaluated by the IRT system for raw score and for variability among scores after transmission of pain scores from the handheld devices to determine randomization eligibility. The IRT system will notify the site if the subject is "Eligible" or "Not eligible." No other information will be provided.

Subjects who continue to meet all entry criteria and are randomized by the IRT system will undergo the following procedures and assessments:

- BPI-DPN
- QOL-DN
- PCS

- Dispensing of study drug Subjects will take their first dose in the clinic. They will be instructed to take the study drug daily and confirm they have taken study drug in past 24 hours in the handheld device upon awakening in morning.
- Re-dispensing/dispensing of rescue medication Subjects will be reminded not to exceed 2 g/day (one to two 500 mg tablets every 6 hours as needed up to 4 tablets total) for DPN related pain.
- Subjects will be reminded of how to record their pain score on the device and will also be reminded about appropriate expectations for their participation in a clinical study and the importance of consistently and accurately reporting their pain intensity throughout the study. Review of these educational materials will be repeated for all subjects at each site-based study visit, with the exception of the final visit. An ongoing blinded data review (e.g., if pain score variability is increased on a subject or site level) will be conducted to monitor these metrics [Analgesic Solutions, Wayland, MA]. On each day until returning to the study site at Week 4/Visit 4, subjects will record the following on the handheld device:
  - At bedtime: average pain intensity, worst pain intensity, average pain upon walking, and rescue medication use during the past 24 hours.
  - Upon waking: DSIS, confirm they have taken study drug.
- The subject will be given a printed copy of the study specific S-STS to take home and complete during the Week 2/Visit 3 telephone or videoconference visit.

# **10.3.** Treatment Period

### 10.3.1. Week 2/Visit 3

Week 2/Visit 3, will be conducted via telephone or videoconference. The following procedures and assessments will be completed:

- Concomitant medication use
- S-STS The subject will be asked to complete the printed copy of the S-STS given to them at their Baseline Visit while communicating with the site staff. The staff will review the subject's answers to the S-STS and recommend corrections, only where the form has been completed incorrectly. The completed S STS source document will be mailed back to the clinic or returned at the next study visit to be filed in the subject's chart and entered into the eCRF system. Adverse events
- MADDERS
- Rescue medication appropriate use assessment by review of daily use entries in the handheld diary as well as by subject interview
- Study drug use and assessment of compliance by review of daily use entries in the handheld diary, as well as by subject interview
- Study drug use and assessment of compliance by review of daily use entries in the handheld diary and by subject interview Compliance with entry into daily diary of pain intensity, rescue medication use, and study drug administration
- Subjects will be instructed to take one capsule of study drug by mouth once daily.

- Subjects will be reminded not to exceed 2 g/day (one to two 500 mg tablets every 6 hours as needed up to 4 tablets total) for DPN related pain.
- Subjects will be reminded of how to record their pain on the device and will also be reminded about appropriate expectations for their participation in a clinical study. Review of these educational materials will be repeated for all subjects within the aLearn® portal at each site-based study visit, with the exception of the final visit. An ongoing blinded data review (e.g., if pain score variability is increased on a subject or site level) will be conducted to monitor these metrics [Analgesic Solutions, Wayland, MA]. On each of day until returning to the study site at Week 4 (Visit 4), subjects will record the following on the handheld device:
  - At bedtime: average pain intensity, worst pain intensity, average pain upon walking, and rescue medication use during the past 24 hours
  - Upon waking: DSIS and confirm they have taken study drug
- A subject may be asked to return to the clinic, per Investigator discretion, for additional study specific training or examination. Any unscheduled return to the clinic should be entered as an Unscheduled Visit into the eCRF and IRT systems.

### 10.3.2. Week 4/Visit 4

At Week 4/Visit 4, the following procedures and assessments will be performed/assessed:

- Concomitant medication use
- S-STS
- Adverse events
- MADDERS
- Vital signs (blood pressure and pulse after sitting or lying supine for at least five (5) minutes)
- Fasting (8 hours) blood samples for serum chemistry and hematology
- Urine sample for urinalysis
- Urine pregnancy test, if clinically indicated for females of childbearing potential
- Urine drug screen
- BPI-DPN
- PGI-C
- QOL-DN
- Rescue medication return and assessment of appropriate use by inventory of returned tablets, as well as by subject interview
- Study drug return and assessment of compliance by inventory of returned capsules, as well as by subject interview
- Compliance with entry into daily diary of pain intensity, rescue medication use, and study drug administration

- Dispensing of study drug Subjects will be instructed to take one capsule of study drug by mouth once daily
- Re-dispensing/dispensing of rescue medication Subjects will be reminded not to exceed 2 g/day (one to two 500 mg tablets every 6 hours as needed up to 4 tablets total) for DPN related pain
- Subjects will be reminded of how to record their pain score on the device and will also be reminded about appropriate expectations for their participation in a clinical study and the importance of consistently and accurately reporting their pain intensity throughout the study. Review of these educational materials will be repeated for all subjects at each sitebased visit, at each site-based visit, with the exception of the final visit. An ongoing blinded data review (e.g., if pain score variability is increased on a subject or site level) will be conducted to monitor these metrics [Analgesic Solutions, Wayland, MA]. On each of day until returning to the study site at Week 8 (Visit 5), subjects will record the following on the handheld device:
  - At bedtime: average pain intensity, worst pain intensity, average pain upon walking, and rescue medication use during the past 24 hours
  - Upon waking: DSIS and confirm they have taken their study drug Subjects will be instructed to return to the study site at Week 8 (Visit 5).

### 10.3.3. Week 8/Visit 5

At Week 8/Visit 5, the following procedures and assessments will be performed/assessed:

- Concomitant medication use
- S-STS
- Adverse events
- MADDERS
- Vital signs (blood pressure and pulse after sitting or lying supine for at least five (5) minutes)
- ECG after at least five (5) minutes in supine position
- Fasting (8 hours) blood samples for serum chemistry and hematology
- Urine sample for urinalysis
- Urine pregnancy test, if clinically indicated for females of childbearing potential
- Urine drug screen
- Compliance with entry into daily diary of pain intensity, rescue medication use, and study drug administration
- Rescue medication return and assessment of appropriate use by inventory of returned tablets, as well as by subject interview
- Study drug return and assessment of compliance by inventory of returned capsules, as well as by subject interview

- Dispensing of study drug Subjects will be instructed to take one capsule of study drug by mouth once daily
- Re-dispensing/dispensing of rescue medication Subjects will be reminded not to exceed 2 g/day (one to two 500 mg tablets every 6 hours as needed up to 4 tablets total) for DPN related pain
- Subjects will be reminded of how to record their pain on the device and will also be reminded about appropriate expectations for their participation in a clinical study. Review of these educational materials will be repeated for all subjects at each site-based visit, with the exception of the final visit. An ongoing blinded data review (e.g., if pain score variability is increased on a subject or site level) will be conducted to monitor these metrics [Analgesic Solutions, Wayland, MA]. On each of day until returning to the study site at Week 12 (Visit 6), subjects will record the following on the handheld device:
  - At bedtime: average pain intensity, worst pain intensity, average pain upon walking, and rescue medication use during the past 24 hours
  - Upon waking: DSIS and confirm they have taken their study drug Subjects will be instructed to return to the study site at Week 12 (Visit 6).

#### 10.3.4. Week 12/Visit 6/Early Termination

At Week 12 (Visit 6) or at the time of early termination from the study, the following procedures and assessments will be performed/assessed:

- Concomitant medication use
- S-STS
- Adverse events
- MADDERS
- Body weight
- Vital signs (blood pressure and pulse after sitting or lying supine for at least five (5) minutes)
- Brief physical examination
- ECG after at least five (5) minutes in supine position
- Fasting (8 hours) blood samples for serum chemistry and hematology, including HbA1c
- Urine sample for urinalysis
- Urine pregnancy test for females of childbearing potential
- Urine drug screen
- BPI-DPN
- PGI-C
- QOL-DN
- PCS

- Compliance with entry into daily diary of pain intensity, rescue medication use, and study drug administration
- Rescue medication return and assessment of appropriate use by inventory of returned tablets, as well as by subject interview
- Study drug return and assessment of compliance by inventory of returned capsules, as well as by subject interview
- Study-issued handheld device and other equipment/documents return
- After completion of the study visits, the site will contact the subjects by telephone within 7-10 days to complete a safety follow-up call. The Investigator, at their discretion, may ask subject to return for an Unscheduled Visit for any safety concerns, abnormal laboratory or ECG findings.
- A final call will be made to the subject approximately 30 days after the final visit to assess for AE closure and any newly reported SAEs.

# 11. STOPPING CRITERIA

Subjects will be withdrawn from the treatment period of the study if any of the following laboratory results and symptoms are observed.

- ALT or AST >8xULN Discontinue subject treatment immediately.
- ALT or AST >5xULN

ALT or AST >3xULN and (TBL >2xULN or INR >1.5)

Discontinue treatment if result is confirmed upon retest (to be done within 48 hours or as soon as feasible).

- ALT or AST >3xULN with the appearance of fatigue, nausea, vomiting, right upper quadrant pain or tenderness, fever, rash, and/or eosinophilia (>5%)
- ALT or AST >3xULN that persists for  $\geq$  4 weeks

If an increase of serum aminotransferase of >3xULN is identified, repeat testing within 48 to 72 hours of all four of the usual serum measures (ALT, AST, ALP, and TBL) should conducted to confirm the abnormalities and to determine if they are increasing or decreasing.

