#### 9.3.5. Clinical Laboratory Assessments

Blood samples for hematology and chemistry will be obtained after an 8-hour fast.

The study investigator should monitor subjects during the study for signs of hepatic abnormality potentially meeting the stopping criteria (Section 11).

The investigator will review clinical laboratory test results as they become available, for determination and documentation of clinical significance (if there are out of range values). The investigative site will contact the medical monitor for any liver function test results that potentially meet the stopping criteria. Possibly drug-related or clinically significant abnormal values of uncertain causality must be repeated. Persistent abnormal laboratory values should be followed at Aptinyx Confidential Page 50 of 74

the investigator's discretion. Abnormal liver function tests (specified in Section 11) must be repeated within 48-72 hours.

Hematology assessments will include hemoglobin, hematocrit, red blood cell count, white blood cell count, differential (neutrophils, lymphocytes, monocytes, eosinophils, and basophils), and platelet count. Hemoglobin A1c will be assessed at Visit 1 and Visit 6/Early Termination.

Chemistry assessments will include glucose, calcium, electrolytes (sodium, potassium, bicarbonate, chloride), phosphorus, blood urea nitrogen (BUN), creatinine, creatinine clearance, albumin, total protein, magnesium, alkaline phosphatase (ALP), aspartate aminotransferase (AST), alanine aminotransferase (ALT), lactate dehydrogenase, gamma-glutamyl transferase (GGT), albumin, total bilirubin, direct bilirubin, indirect bilirubin, uric acid, and C-reactive protein (CRP). Triglycerides and a thyroid panel (TSH, T3, T4, and free T4) will also be measured at Visit 1.

Qualitative urinalysis will include pH, specific gravity, glucose, ketones, protein, blood, leukocyte esterase, urobilinogen, nitrites, and reflex microscopy.

Abnormal clinical laboratory tests at screening may be repeated, on a case by case basis, after consultation with the Medical Monitor.

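### The liver stopping rule uses INR >1.5, but no listed panel, visit or named retest obtains an INR, so that limb acts only if someone adds the test ad hoc

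*Protocol*

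**What the plan says.** Protocol Section 11 lists laboratory and symptom findings that lead to withdrawal from treatment. One is "ALT or AST >3xULN and (TBL >2xULN or INR >1.5"), followed by the action: "Discontinue treatment if result is confirmed upon retest (to be done within 48 hours or as soon as feasible"). A separate sentence in the same section covers any aminotransferase above 3xULN. It calls for a repeat at 48 to 72 hours of "all four of the usual serum measures (ALT, AST, ALP, and TBL").

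Protocol Section 9.3.5 lists the tests. The liver part of the chemistry panel is "alkaline phosphatase (ALP), aspartate aminotransferase (AST), alanine aminotransferase (ALT), lactate dehydrogenase, gamma-glutamyl transferase (GGT), albumin, total bilirubin, direct bilirubin, indirect bilirubin". Hematology ends with "differential (neutrophils, lymphocytes, monocytes, eosinophils, and basophils), and platelet count". The same section says the investigator "should monitor subjects during the study for signs of hepatic abnormality potentially meeting the stopping criteria (Section 11") and that the site will "contact the medical monitor for any liver function test results that potentially meet the stopping criteria". It adds: "Abnormal liver function tests (specified in Section 11) must be repeated within 48-72 hours".

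On the analysis side, SAP Section 6.2.25 flags subjects by ALT, AST and bilirubin. SAP Section 6.12.2 promises a separate listing of those three for flagged subjects, a listing of all out-of-range laboratory values, and a listing of all laboratory assessments. SAP Section 11 has two table titles for coagulation data (14.3.7.5 and 14.3.7.6).

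**The concern.** A mandatory safety rule needs the measurement it is written on. Here the rule names INR, but the sections that say what blood is drawn do not. A site that does exactly what the protocol lists will have no INR to compare with 1.5. A subject whose only qualifying finding would be a raised INR then stays on drug, unless the investigator orders the test or withdraws the subject on judgement.

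The liver rules deserve to work in this trial. Protocol Section 4 reports raised liver enzymes and microscopic liver changes in dogs, judged adverse at 240 mg/kg/day, and increased ALT among the commonest adverse events. One earlier subject on 10 mg met stopping criteria through raised ALT and AST, and another had raised GGT, ALT and AST during the 200 mg period. Earlier dosing is described as up to 4 weeks; this trial doses for 12, with acetaminophen rescue up to 2 g/day. None of this shows that an INR-only case is likely. Section 4 also puts exposure at the dog no-adverse-effect level at about 70 times that of the 50 mg human dose.

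**Working it through.** The check is a cross-reading of the documents. There is no planned figure to reproduce.

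**Step 1. Where could an INR come from?**

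- Section 9.3.5 hematology, chemistry and urinalysis lists: no PT, INR or other coagulation test.
- Table 3 laboratory row: hematology, chemistry and urinalysis only. Footnote j adds HbA1c, triglycerides, HIV, hepatitis B and C, CRP and thyroid tests at Visit 1, and HbA1c at Visit 6. No INR.
- Section 10 visit lists: no coagulation sample.
- Scheduled draws are at Visits 1, 2, 4, 5 and 6, which is 5; INR is listed at 0 of 5. Visits 1 and 2 precede the first dose and Week 12 ends dosing. The draws at which a stopping rule can still prevent later scheduled doses are therefore Weeks 4 and 8, which is 2 of 5.
- Named retest: 4 measures, of which INR is 0.

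INR appears once in the two documents, in the stopping rule itself. It is not in the protocol's abbreviation list.

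**Step 2. Is INR an exception?** The Section 11 rules use five laboratory quantities: ALT, AST, TBL, eosinophils and INR. Section 9.3.5 lists the first four, so 5 − 4 = 1 is missing.

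**Step 3. Which triggers work from the listed tests?**

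| Section 11 trigger | Needs | Available from listed tests |
|---|---|---|
| ALT/AST >8xULN | ALT, AST | yes |
| ALT/AST >5xULN | ALT, AST | yes |
| >3xULN with TBL >2xULN | ALT, AST, TBL | yes |
| >3xULN with INR >1.5 | ALT, AST, INR | no INR |
| >3xULN with listed symptoms or eosinophilia | ALT, AST, differential, clinical review | yes |
| >3xULN for at least 4 weeks | serial ALT, AST | yes |

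That is 5 of 6. The protocol writes the third and fourth rows as one criterion. On its own count there are five criteria, four fully evaluable and one evaluable through bilirubin only.

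**Step 4. Who is left?** Removing everyone whom another row would catch leaves subjects with ALT/AST >3x to 5xULN, TBL not >2xULN, no listed symptoms or eosinophilia, and elevation under 4 weeks. The 48 to 72 hour repeat would show a rise above 5xULN or TBL >2xULN within 2 to 3 days, so those routes stay covered.

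**Step 5. How long could it matter?** The persistence criterion takes over at 4 weeks. Week 4 to Week 8 is 56 − 28 = 28 days, and Week 8 to Week 12 is 84 − 56 = 28 days (nominal, before the visit windows). For an elevation first seen at Week 8, dosing nominally ends at about the time the persistence criterion could act.

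**The case against.** The best defence is that Section 11 holds two instructions. The INR criterion carries its own confirmation clause, and a result that includes INR can be confirmed only by measuring INR. The four-measure repeat is a separate sentence and does not forbid further tests. Section 9.3.5 directs the investigator to the Section 11 criteria and to the medical monitor, and Section 7.4 allows withdrawal for a laboratory abnormality on the investigator's judgement. The SAP plans coagulation tables, including normal-range shifts, which presuppose baseline and later values.

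Part of this stands. An INR may well be ordered, so it would be too strong to say that the limb can never be evaluated. What does not stand is the idea that the text supplies the first INR. Confirmation and repetition both need an initial result, the duty to call the medical monitor depends on a result that may meet the criteria, and no listed test produces an INR. Section 7.4 is discretion, whereas Section 11 is mandatory. The coagulation titles name no parameter, match no protocol sample and have no visible counterpart among the SAP 16.2.8 listings. They are an inconsistency, not a sampling instruction.

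A reader might also infer that the SAP would lose an INR that was ordered, because the liver listing covers only ALT, AST and bilirubin. The documents do not support this. SAP Section 6.12.2 lists all laboratory assessments and all out-of-range values. Anyone eligible for the INR limb has ALT/AST >3xULN and is therefore already flagged under SAP Section 6.2.25.

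**Conclusion.** The point holds, and it is minor. The protocol makes confirmed ALT/AST >3xULN with INR >1.5 a reason for withdrawal but specifies no PT/INR sample, so as written this limb depends on an ad hoc test. Its reach is the group in Step 4 of the working. The documents give no rate for that group. No efficacy conclusion changes.

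Two stronger readings should be resisted. One is that the combined criterion, or the liver stopping rules as a whole, do not work; the bilirubin alternative and all the other triggers do. The other is that no INR is measured in the trial. What the central laboratory actually runs is not stated, and the coagulation table titles leave it open. Confidence is high for the omission from the text and cannot be high for a gap in practice.

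**What to change.** In Protocol Section 11, change the repeat testing for ALT/AST >3xULN to ALT, AST, ALP, TBL and PT/INR, and say the same in Section 9.3.5. Because ALT/AST >3xULN is a precondition of the INR limb, this repeat reaches the subjects who need the test.

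Then state what counts as confirmation. If ALT/AST is still >3xULN and this first INR is >1.5, hold study drug, repeat the INR within 48 hours or as soon as feasible, and withdraw if it is confirmed. Withdrawing on the first INR alone would change the rule, since Section 11 asks for confirmation. The hold is an added step; Section 9.4.3.2 already has an action code for interruption.

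Add that INR is to be interpreted in light of any anticoagulant use. Anticoagulants are not among the prohibited medications in Sections 8.7 and 15.1, and concomitant medication is recorded at every visit. A baseline PT/INR for everyone would help that interpretation but is not needed to make the limb work.

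The cost is wording in two protocol sections, one extra tube at a retest already required, and a second INR draw for those with a first value above 1.5. Adding INR to SAP listing 14.3.4.1 and reconciling tables 14.3.7.5 and 14.3.7.6 with what is collected are optional housekeeping.
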